3.3 Sample size justification

The sample size of the study is calculated based on results from literature [5-8]. Evaluation of the efficacy for this study is being accomplished through estimation of a 95% confidence interval. No hypotheses are specified for this study and no p-values are being calculated but for descriptive purposes, therefore no level of significance is specified.

Considering a randomization ratio 1:1 (reparixin vs. placebo), a sample size of 60 evaluable subjects is considered adequate for assessing the difference between groups in primary endpoints, i.e., change from baseline in OI at day 7 and VFD at day 28.

The given sample size will provide a reasonable precision in the estimation of group differences in primary endpoints to an expected margin of error for a 95% one-sided confidence interval of at most 46.5% the standard deviation, whatever it is:

Standard/Forms/Template				
Title		Statistical Analysis Plan Template		
Code		Version	Effective Date	Page
PPD		01	29 Aug 2022	20 of 78

- Assuming a standard deviation of 11.5 points for OI, the 95% one-sided confidence interval for the difference between groups will have a width of 5.35 points;
- Assuming a standard deviation of 8 days for VFD, the 95% one-sided confidence interval for the difference between groups will have a width of 3.75 days.

If 10% of enrolled patients will not be evaluable for primary analysis, the total number of patients to be enrolled will be approximately 66.

3.4 Randomization and blinding

3.4.1 Randomization

Enrolled patients will be randomized in a 1:1 ratio to either reparixin or placebo according to the stratified randomization list. Dropouts after randomization will not be replaced.

The permuted block randomization list will be generated with a computer procedure by a CRO independent statistician not involved in the conduct of the study and will be provided to Dompé in a sealed envelope to prevent unblinding. The facility responsible of IMP packaging/labelling will also receive appropriate randomization codes for the purpose of IMP preparation.

Randomization will be performed through Interactive Response System (IRS). Each Patient Kit number will be randomly associated with a treatment group. Access to individual patient treatment code will be allowed only in the event of a medical emergency where the knowledge of patient treatment is required to provide the patient with appropriate care. The investigator and Dompé Pharmacovigilance will have access to the randomization code for a specific patient in case of a medical emergency or for safety reasons. Unblinding events will be recorded and reported in the Clinical Study Report (CSR). The treatment assignment information will be kept confidential and will not be disclosed to any other.

Once the study has been completed and the database has been locked, the treatment assignment information will be accessible to the study biostatistician(s) who will perform the statistical analyses and will generate reports.

3.4.1.1 Stratification factors

Randomization list will be stratified by site. Site is also included in the statistical model, as random effect, for the analysis of the primary efficacy endpoints (section 7.1.1.1)

Given the high number of sites and the relatively small number of patients per site, a pooling strategy will be considered as an option to be applied at the time of the Blinded Data Review Meeting.

In case there will be specific groups of Standard Of Care identified across sites, these will be grouped and the new stratification factor to consider for the analysis would become "Standard of Care". This option will be discussed during the Blind Data Review Meeting.

3.4.2 Unblinding

Appearance, including packaging and labelling, of the IMP (tablets, packaging) will not allow to recognize actual treatment (either reparixin or placebo).

Standard/Forms/Template				
Title		Statistical Analysis Plan Template		
Code		Version	Effective Date	Page
PPD		01	29 Aug 2022	21 of 78

For each randomized subject, individual code breaks will be accessible in the event of a medical emergency requiring knowledge of the treatment assigned to the subject. Only the responsible investigator, or authorized delegates, can break the code via the Interactive Response System (IRS). Investigators will be allowed to unblind study medication directly through the Interactive Response Technology (IRT) system; any unblinding must be notified to the CRO's medical monitor. Training is provided to investigators prior to authorization to use the IRT system and the unblinding function is outlined in the study specific user guide.

Dompé Pharmacovigilance, Safety and Surveillance Department shall break the treatment code for subjects who experience a Suspected Unexpected Serious Adverse Reaction (SUSAR), in order to determine if the individual case requires expedited regulatory reporting and fulfils expedited regulatory reporting requirements. Unmasked information will not be disclosed to Investigators and other Sponsor staff.

With the exception of the above-mentioned episodes, the identity of the treatments will remain unknown to the subject, investigator, site staff, CRO and Dompé's personnel until the study completion and formal unmasking. Only the Data Monitoring Committee (DMC) will have access to group-unblinded and/or fully unblinded DMC reports.

For analysis purposes, the randomization codes will be broken when the last enrolled patient has completed therapy, and once the database has been locked.

3.5 Efficacy endpoints

This section lists all study endpoints together with the clarification on the study day to be considered for each endpoint.

3.5.1 Primary endpoint

- Change in oxygenation index (OI) from baseline to day 7 [study day: date/time]
OI defined as: % mean airway pressure x FIO₂/PaO₂ (A difference between groups in 7-days OI of 6.6 points was significantly associated with 28-days mortality (Go et al., 2016). Thus, such a difference in the change in 7-days OI, ranked as the most important endpoint, will be valued as a proxy of clinical success)
- Ventilator free days (VFD) at day 28 [study day: date/time]

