4.4 Estimands

4.4.1 Primary estimands

The primary estimand #1 is defined by the following attributes:

- Population: Adult patients hospitalized for Acute Respiratory Distress Syndrome, as defined by the inclusion-exclusion criteria of the study.
- Variables: Oxygenation index (OI) at baseline and at day 7.
- Intercurrent events:
 - Death before Day 7, or at Day 7 if OI is not present, as a terminal event which precludes the observation of the variable, will be handled by the composite strategy. Day 7 value is derived using Study Day based on Date (i.e., Day 7= First IMP Intake + 6), since only date of death is collected. The event will be included in the estimand by imputing for OI at day 7, an extreme unfavorable value characterizing the treatment failure. The 90°

Standard/Forms/Template				
Title		Statistical Analysis Plan Template		
Code		Version	Effective Date	Page
PPD		01	29 Aug 2022	28 of 78

percentile of the distribution of the observed values will be used (the value will be rounded to present only one decimal place only for data presentation, not for imputation).

- For patients that at day 7 are extubated and OI is not evaluable, extubation will be handled by the composite strategy as an event which precludes the observation of the variable of interest. The event will be included in the estimand by imputing for OI at day 7 a sufficiently extreme favorable value characterizing the treatment success. The 10° percentile of the distribution of the observed values will be used (the value will be rounded to present only one decimal place, only for data presentation, not for imputation). A patient is extubated at day 7 if the patient results not intubated in the time range [First IMP Intake Date/Time +132h, First IMP Intake Date/Time +155h and 59 min].
- Treatment discontinuation, which may affect interpretation of the variable, will be handled by the treatment policy strategy. The occurrence of the intercurrent event will be irrelevant. All observed values will be used regardless of occurrence of the intercurrent event. Retrieved dropouts will be used for data imputation of all missing data (not due to death and not due to extubation), whichever is the reason of missingness.
- Population-level summary: Change in oxygenation index (OI) from baseline to day 7

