7.1.3.5 Additional clinically relevant adjustment(s)

The analysis of the two primary endpoints described in section 7.1.1 will be entirely reproduced after updating the regression model used for the analysis with further clinically relevant variables that may result imbalanced at baseline (for example specific comorbidities). This decision will be taken at the BDRM (keeping the study team blinded) or after the database lock (in this case the analyses will be considered as ad-hoc).

The following supplementary analysis will be performed only for the primary endpoint referred to change in OI from baseline to day 7.

7.1.3.6 Change in OI from baseline to Day 7 without imputing death and extubation.

This analysis will be performed only on the subset of complete cases only (i.e., without considering patients with missing endpoint) that reached Day 7 still intubated (imputed values of patients who died or were extubated before or at Day 7 with no OI at Day 7 will be classified as missing). Value and change in OI from baseline to Day 7 will be analyzed by means of descriptive statistics as a continuous variable. Comparison between treatments will be performed by means of two-sample t-test and, if assumptions of normality is not confirmed, two-sample Mann-Whitney U test (alpha=0.05 one-sided).

Standard/Forms/Template				
Title		Statistical Analysis Plan Template		
Code		Version	Effective Date	Page
PPD		01	29 Aug 2022	48 of 78

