Primary endpoint "Change in oxygenation index (OI) from baseline to day 7 " [study day based on Date/time]	
OI derivation
 
OI is defined as: % mean airway pressure x FIO2/PaO2, derived as 100 x mean airway pressure x FIO2/PaO2. Following the estimand definition:
 
 - If patient dies before Day 7, or at Day 7 (Day 7 date = Day 1 date + 6, since only date of death -no time- is collected) and OI is missing: OI at day 7 = 90th percentile of the distribution of the primary variable at Day 7. - If patient at Day 7 is extubated* and OI is not evaluable (i.e., if the patient results not intubated* in the time range [First IMP Intake Date/Time +132h, First IMP Intake Date/Time +155h and59 min]): OI at day 7 = 10th percentile of the distribution of the primary variable at Day 7. - Otherwise, OI is set to missing. 
*intubation/extubation status at day 7: check intubations in "Extubation Summary" CRF form. Use the multiple entries of extubation/re-intubation: if the last record of intubations/extubation prior day 7 is an extubation and there are no intubations at day 7, it means the subject was extubated on Day 7. Subjects should reach day 7 to be eligible for this imputation.
 
Collection of data on FiO2/PaO2 and mean airway pressure
 
The implementation of the OI is based on 2 daily forms: "Mechanical Ventilation Parameters" for mean airway pressure, and "Lung Function" for the following parameters: PaO2/FIO2, FIO2, PaO2. FIO2/PaO2, used for the computation of OI, may be derived as 1/(PaO2/FIO2) or by using the individual values of PaO2 and FIO2 (when PaO2/FIO2 is missing) as described in the following section "Missing PaO2/FiO2 or mean airway pressure".
 
Missing PaO2/FiO2 or mean airway pressure
 
In case of missing PaO2/FiO2 for a specific visit, derive it based on the individual values of PaO2 and FiO2, if available. If PaO2 is not available set to missing (PaO2 won't be derived). The same applies for mean airway pressure, if not collected on a specific visit, the OI will be missing for that day.
 
Baseline derivation
 
1 - For each assessment performed on or prior treatment start date/time, derive OI as defined below.
 
1.1 Select the last record of mean airway pressure collected in that day (if on the same date of treatment start date, use only records with time <= time of first exposure to IMP)
 
1.2 - Select the "FiO2/PaO2" which is closest (and non missing) to the selected "mean airway pressure" and occurring on the same timeframe (but assessed on or prior treatment start date/time). Same timeframe here means that it should be considered the date/time of mean airway pressure (detected in step 1.1) +/- 12 hours BUT always considering prior to the first IMP intake. If there is any FiO2/PaO2 available in this timeframe, take that FiO2/PaO2 assessment. If there is no FiO2/PaO2 available in this timeframe, select the FiO2/PaO2 collected in the same exact date of the selected mean airway pressure (selected in step 1.1). If there is no such match, the OI baseline will set as missing.

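### The 6.6-point mark of clinical success in SAP 3.5.1 was not set on the scale of the OI co-primary that it judges, because that endpoint scores death and extubation as percentiles of this trial's own Day 7 values

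*SAP*

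**What the plan says.** SAP 3.5.1 lists the change in OI to Day 7 as the first co-primary and gives only the formula: "OI defined as: % mean airway pressure x FIO₂/PaO₂". In the same parenthesis it states that "A difference between groups in 7-days OI of 6.6 points was significantly associated with 28-days mortality" and concludes that "such a difference in the change in 7-days OI, ranked as the most important endpoint, will be valued as a proxy of clinical success". I find the figure 6.6 nowhere else in the readable text of either document.

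The analysed variable is built elsewhere. SAP 4.4.1 handles death by Day 7 (with no Day 7 OI) by a composite strategy, assigning "an extreme unfavorable value characterizing the treatment failure"; Table 3 in SAP 11.1.1 makes this "OI at day 7 = 90th percentile of the distribution of the primary variable at Day 7". For patients extubated at Day 7 whose OI cannot be evaluated, 4.4.1 says "The 10° percentile of the distribution of the observed values will be used" and Table 3 says "OI at day 7 = 10th percentile of the distribution of the primary variable at Day 7". SAP 7.1.1.1 keeps these scores in the Day 7 summary statistics and reports the adjusted difference with a two-sided 90% CI.

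Two further places matter. The one-sentence summary that closes Estimand #1 in SAP 4.4.1 describes patients who are alive up to Day 7 and intubated then, which is not the composite population. SAP 7.1.3.6 adds a supplementary analysis of measured OI only, in which "imputed values of patients who died or were extubated before or at Day 7 with no OI at Day 7 will be classified as missing"; no benchmark is attached to it.

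**The concern.** The benchmark stands beside a physiological formula. The endpoint it is applied to mixes measured OI with two scores taken from this trial's own data, so an externally cited 6.6 cannot have been calibrated to it. The two scales can part in either direction. A given difference in measured OI is diluted, because the dead and the extubated carry fixed scores. The composite also moves when deaths or extubations differ between arms, even if no measured OI changes.

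The trial is designed for estimation and specifies no hypothesis (SAP 3.3), so its conclusion rests on how the estimate is read. This is the plan's only numerical mark of success, and it is attached to the endpoint the SAP ranks first. A reader holding the composite estimate against 6.6 could draw too weak or too strong a conclusion about oxygenation.

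**Working it through.** **Inputs from the documents.** Benchmark 6.6 points (SAP 3.5.1). SD for OI 11.5 points (SAP 3.3). Death score P90 and extubation score P10 of Day 7 OI (SAP 4.4.1, 11.1.1). The 6.6 is a cited value and cannot be derived here; it equals 6.6/11.5 = 0.57 SD. The stated precision for OI, 0.465 × 11.5 = 5.35 points, does not use it.

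**Assumptions, not in the documents.** At Day 7, 10–20% dead and 15–40% extubated, hence 40–75% with a measured OI. Percentiles are taken over both arms together: neither section mentions arm, and I read them as pooled. Baseline OI is balanced, so a difference in change equals a difference in Day 7 level. For step 2, measured OI is lognormal with mean 12–18 and SD 11.5.

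**Formula.** With shares m (measured), d (dead) and e (extubated), m + d + e = 1, the mean Day 7 score in an arm is m·μ + d·P90 + e·P10, where μ is mean measured OI. For equal m in both arms, the difference between arms is

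m × (difference in μ) + (difference in d) × P90 + (difference in e) × P10.

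**Step 1: equal death and extubation shares.** The last two terms vanish. The result does not depend on the mean or distribution of OI.

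| m | 6.6 measured becomes (6.6 × m) | Measured difference needed for 6.6 (6.6/m) | In SD of 11.5 |
|---|---|---|---|
| 0.75 | 4.95 | 8.8 | 0.8 |
| 0.60 | 3.96 | 11.0 | 1.0 |
| 0.50 | 3.30 | 13.2 | 1.1 |
| 0.40 | 2.64 | 16.5 | 1.4 |

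**Step 2: no difference in measured OI, 10 percentage points of patients moved from death to extubation in one arm.** The shift is 0.10 × (P90 − P10).

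- Mean 12: 0.10 × (24.3 − 3.1) = 2.1
- Mean 15: 0.10 × (28.4 − 5.0) = 2.3
- Mean 18: 0.10 × (32.1 − 7.2) = 2.5

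A simulation with normal or lognormal OI and larger imbalances (extubated 15% vs 40%, dead 20% vs 5%) gave composite differences of 4.1 to 5.9 points with no difference in measured OI.

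**Step 3: both at once.** Add the 2.1–2.5 points from step 2 to a measured difference of 6.6.

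- m = 0.40: 2.64 + 2.1 to 2.5 = about 4.7 to 5.1
- m = 0.60: 3.96 + 2.1 to 2.5 = about 6.1 to 6.5
- m = 0.75: 4.95 + 2.1 to 2.5 = about 7.1 to 7.5

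This uses the P90 − P10 spread from the case of no measured difference. With a 6.6-point separation the simulated spread is slightly wider (22.8, 25.1 and 26.5 for the three means), which adds about 0.2. The same measured effect can therefore land below, near or above 6.6. If deaths go the other way (10% on placebo, 20% on reparixin, 20% extubated in both), the simulated composite difference for a measured 6.6 is only 2.7 to 2.9.

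**The case against.** The strongest reply is that 6.6 decides nothing. It appears once, in a parenthesis; SAP 3.3 specifies no hypothesis and treats p-values as descriptive; no CI limit, power calculation or stopping rule uses it. That stands, and it confines the point to interpretation.

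Second, a reader might infer that a drug with exactly the target effect would be declared a failure. The documents do not support that. They set no target effect and make no such declaration, and the shortfall in step 1 holds only if death and extubation shares are equal. A drug that improves oxygenation may well change those shares too, and step 3 shows the total can then reach or pass 6.6.

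Third, it is tempting to call the mortality justification circular because deaths are scored inside the endpoint. The cited association comes from an external study, and scoring this trial's deaths does not make that association circular.

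Fourth, the documents do not say how the cited study treated deaths and extubations before Day 7, so it cannot be asserted that its 6.6 was purely a measured difference. What can be said is that SAP 3.5.1 gives only the formula, and that scores taken from this trial's percentiles cannot have been part of the cited figure.

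Finally, some of the remedy exists. SAP 7.1.3.6 reports measured OI, SAP 8.1 tabulates deaths by day, VFD reflects liberation from ventilation, and 7.1.1.1 is open about the imputed scores. All true, but none of it says which OI result the 6.6 judges, and the closing sentence of Estimand #1 adds to the doubt.

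**Conclusion.** The mismatch is real and follows from the SAP's own text: the benchmark is stated for OI as a formula and applied to a composite on a different scale. On the assumed 40–75% measured, with equal event shares and pooled percentiles, a measured 6.6 becomes about 2.6–5.0. A shift of 10 percentage points from death to extubation moves the composite by about 2.1–2.5 with oxygenation unchanged. The direction of the net discrepancy cannot be known in advance, and the two scales agree in general only if nearly everyone is alive and intubated at Day 7. The Day 7 shares and the OI mean and distribution are assumptions; the multiplication by the measured fraction needs only the shares, pooling and balanced baselines. Type I error and the planned estimates are unaffected. What changes is what a composite difference near 6.6 may be said to mean.

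**What to change.** 1. In SAP 3.5.1, remove the statement that a 6.6-point difference in the co-primary counts as a proxy of clinical success. If 6.6 is mentioned at all, attach it only to the measured-OI analysis in 7.1.3.6 and label it descriptive, in a subset selected after randomization (alive and still intubated). That is a weak place for a between-arm benchmark, so deletion is cleaner.
2. Interpret the composite by its adjusted difference and 90% CI, and show beside it, per arm, the proportions dead, extubated and measured at Day 7.
3. Reword the closing sentence of Estimand #1 in SAP 4.4.1 so that it agrees with the composite strategy set out just above it.

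The cost is SAP wording and one descriptive table row; no data collection or model changes. The sponsor gives up a convenient success figure for the composite.

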3.5.2 Secondary efficacy endpoints

The following secondary endpoints will be considered.

- Change in OI from baseline to day 4 [study day: date/time]

Standard/Forms/Template				
Title		Statistical Analysis Plan Template		
Code		Version	Effective Date	Page
PPD		01	29 Aug 2022	22 of 78

- Acute lung injury score [composite of PaO₂/FIO₂ ratio, PEEP, lung compliance (plateau airway pressure minus PEEP/TV) and extent of pulmonary infiltrates] at 2, 3, 7, 14 days (if still intubated) [by visit and date/time]
- SOFA scores at 2, 3, 7, 14 days (if still intubated) [study day: date/time]
- Ventilatory ratio at 2, 3, 7, 14 days (if still intubated) [study day: date/time]
- Incidence of ECMO at day 14 [study day: date]
- Use of vasoactive medications at day 14 [study day: date/time]
- Change from baseline of CXR assessment of pulmonary edema by “radiographic assessment of lung edema” (RALE) score at 2, 3, 7, 14 days [by visit]
- Percentage of patients achieving pressure support ventilation equal to 5 cmH₂O with PEEP equal to 5 cmH₂O for 2 hours (measure of weaning) by day 28 and hospital discharge [study day: date]
- ICU-free days by day 28 and hospital discharge [study day: date]
- Hospital-free days by day 28 [study day: date]
- Incidence of tracheostomies by day 28 and hospital discharge [by visit]
- Incidence of LTAC facility by day 28 and hospital discharge [by visit]
- All-cause mortality by day 28 [study day: date]
- Hospital discharge by day 28 [study day: date]
- All-cause mortality by day 60 [study day: date]
- Change from baseline to day 3, 7 and 14 in plasma levels of IL-6, IL-8, PAI-1, Plasma TNFr-1, ICAM-1, RAGE [by visit]

3.6 Safety endpoints

- Haematology/biochemistry tests change from screening to day 3±8h, 7±1, 14±2, 21±2 (if still receiving reparixin), 28±2 visits and at hospital discharge [by visit]
- eGFR, absolute value and change from screening to day 3±8h, 7±1, 14±2, 21±2 (if still receiving reparixin), 28±2 visits and hospital discharge [by visit]
- Hepatic Function (ALT/AST, total/direct bilirubin), absolute values and change from screening to day 3±8h, 7±1, 14±2, 21±2 (if still receiving reparixin) visits and at hospital discharge [by visit]

Standard/Forms/Template				
Title		Statistical Analysis Plan Template		
Code		Version	Effective Date	Page
PPD		01	29 Aug 2022	23 of 78

- ECG/rhythm analysis changes from screening to day 3 ± 8 h, 7 ± 1 , 14 ± 2 , 21 ± 2 (if still receiving reparixin), 28 ± 2 visits and hospital discharge. [by visit]
- Incidence of secondary infections defined as new (occurring after the first IMP intake) infection in a previously known to be sterile site, including blood, body fluid or tissue, or new pathogen isolated from cultures of biological samples known to be previously infected by day 28 [study day: see section 11.1.1]
- Incidence of TEAEs and TESAEs from the beginning of study treatment to up to the end of study participation.
- Vital Signs change from baseline to daily assessment through extubation (namely, day 1, day 2, day 3, day 7, day 14, day 21) [study day: date/time]

4. Statistical Analysis

